16.1.1. ALL TEAES

Incidence of TEAEs will be presented by System Organ Class (SOC) and Preferred Term (PT) and broken down further by maximum severity and relationship to study medication.

16.1.1.1. Severity

Severity is classed as mild/ moderate/ severe (increasing severity). TEAEs starting after the first dose of study medication with a missing severity will be classified as severe. If a patient reports a TEAE more than once within that SOC/ PT, the AE with the worst-case severity will be used in the corresponding severity summaries.

16.1.1.2. Relationship to Study Medication

Relationship, as indicated by the Investigator, is classed as "yes" or "no". A related TEAE is defined as a TEAE with a relationship to study medication as "yes". TEAEs with a missing relationship to study medication will be regarded as relationship = "yes" to study medication. If a patient reports the same AE more than once within that SOC/ PT, the AE with the worst-case relationship to study medication will be used in the corresponding relationship summaries.

16.1.2. TEAES LEADING TO DISCONTINUATION OF STUDY MEDICATION

TEAEs leading to permanent discontinuation of study medication will be identified by using the question "Did the AE cause the Patient to discontinue from the study?" from the AE page of the eCRF.

For TEAEs leading to discontinuation of study medication, summaries of incidence rates (frequencies and

Document: Z:\RPL554\UYA25849\Biostatistics\Documentation\SAP\Verona RPL554-CO-204 SAP v1.0

Author: [name] Version Number: 1.0

Version Date: [18OCT2018]

Template No.: CS_TP_BS016 Revision 5 Reference: CS_WI_BS005

Effective Date: 01Apr2018

Page 37 of 50

percentages) by SOC and PT will be prepared.

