4.3 Removal of Patients from Therapy or Assessment

4.3.1 Study Treatment Discontinuation

Study treatment must be discontinued for the following reasons:

- Unacceptable toxicity related to study treatment
- Intolerable or persistent adverse events of any severity
- General or specific changes in the patient's condition rendering the patient unacceptable for further treatment in the judgment of the Investigator
- Clinically significant progression of disease
- Pregnancy in a female patient

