7.4.1.2 Recording and Assessing Adverse Events

All adverse events, whether reported spontaneously by the patient, in response to open questioning on treatment days or observed by the Investigator or his/her staff, will be recorded from informed consent until the end of study visit. The start and stop time will be recorded and adverse events will be assessed by the Investigator for the following:

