7.4.1.2.4 Action and Outcome

• Action taken with study medication (none, study medication stopped, study medication temporarily interrupted)

Verona Pharma plc CONFIDENTIAL Page 42 of 66

- Other actions (none, concomitant medication, study discontinuation, hospitalization, other)
- The outcome and date of outcome according to the following definitions:
 - Recovered or resolved (adverse event disappeared)
 - Recovering or resolving (patient is recovering)
 - Not recovered or not resolved (adverse event remains without signs of improvement)
 - Recovered or resolved with sequelae (adverse event has resulted in permanent disability or incapacity)
 - Fatal
 - Unknown (only applicable if patient has been lost to follow-up)
- Seriousness (yes or no)

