8.3 Data Management and Coding

Data for each patient will be recorded in an eCRF. Data collection must be completed for each patient who signs an informed consent form and receives at least one dose of study medication.

eCRFs will be designed and produced by the Sponsor or designee and should be completed in accordance with instructions. The Investigator is responsible for maintaining adequate and accurate medical records from which accurate information will be transcribed directly into the eCRFs using a secure internet connection. The eCRFs should be filled out completely by the Investigator or designee as stated on the delegation of responsibilities form. The eCRF system will be Food and Drug Administration Code of Federal Regulations 21 Part 11 compliant.

The eCRFs must be reviewed, signed and dated by the Investigator.

Data entered into the eCRF will be validated as defined in the data validation plan. Validation includes, but is not limited to, validity checks (e.g. range checks), consistency checks and customized checks (logical checks between variables to ensure that study data are accurately reported) for eCRF data and external data. A majority of edit checks will be triggered during data entry and will therefore facilitate efficient 'point of entry' data cleaning.

Data management personnel will perform both manual eCRF review and review of additional electronic edit checks to ensure that the data are complete, consistent and reasonable. The electronic edit checks will run continually throughout the course of the study and the issues will be reviewed manually online to determine what action needs to be taken.

Manual queries may be added to the system by clinical data management or study monitor. Clinical data managers and study monitors are able to remotely and proactively monitor the patient eCRFs to improve data quality.

External data (laboratory safety, Holter, 12-lead ECG and pharmacokinetic data) will be transferred electronically into the study database. Discrepancies will be queried to the site and/or the laboratory until the electronic data and the database are reconciled.

All updates to queried data will be made by authorized study center personnel only and all modifications to the database will be recorded in an audit trail. Once all the queries have been resolved, eCRFs will be locked by password protection. Any changes to locked eCRFs will be approved by the Investigator.

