9.4.7 Safety

Safety data including safety laboratory tests, 12-lead ECG and Holter parameters, vital signs and physical examinations, will be summarized by treatment group and time point of collection, when appropriate. For continuous variables, the change from baseline (pre-dose at each treatment period) to each post-dose time point will also be calculated and summarized. Data will further be illustrated by shift tables (showing changes from low/normal/high) and shift

Verona Pharma plc CONFIDENTIAL Page 51 of 66

plots for selected time points. Separate listings will be generated of abnormal values occurring after the first dose of study treatment.

Coded adverse event terms will be presented by system organ class (SOC) and preferred term and summarized by treatment group. A summary table by treatment group with total number and number of patients with adverse events, SAEs, adverse events leading to discontinuation of study treatment, causally related adverse events and severe adverse events will be produced. Further, SAEs, causally related adverse events and adverse event of each intensity will be summarized by SOC and preferred term.

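### SAP 16.1.2 identifies adverse events leading to discontinuation of study medication by a question about leaving the study, so the summary can misclassify events in either direction.

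*SAP*

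**What the plan says.** Under a title about discontinuation of study medication, SAP 16.1.2 states that "TEAEs leading to permanent discontinuation of study medication will be identified by using the question" on the AE page of the eCRF: "Did the AE cause the Patient to discontinue from the study". Incidence by system organ class and preferred term is then built on that answer. No other variable enters the definition.

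The protocol treats the two ideas as separate items. Section 7.4.1.2 says that "adverse events will be assessed by the Investigator for the following", and the list in 7.4.1.2.4 contains both of these:

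- "Action taken with study medication (none, study medication stopped, study medication temporarily interrupted"
- "Other actions (none, concomitant medication, study discontinuation, hospitalization, other"

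Stopping treatment has its own section, 4.3.1, which opens "Study treatment must be discontinued for the following reasons". Patient withdrawal is covered in 4.3.2. For reporting, protocol 9.4.7 includes "adverse events leading to discontinuation of study treatment" among the lines of the AE summary. SAP 3.3 declares no changes from the protocol's analysis.

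**The concern.** The label of the summary concerns the drug and its source variable concerns the study. A patient can in principle have study medication stopped for an adverse event and not be recorded as leaving the study, or leave the study because of an adverse event when no dosing was under way. In either case the answer to the question does not describe what the table says it describes.

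Tolerability and safety are a secondary objective, and two RPL554 doses are set against placebo in about 70 patients. If events of this kind are few, which the documents neither state nor rule out, a single misclassified event could move one treatment's count from zero to one or the reverse. The summary would also not be the one that protocol 9.4.7 asks for, with no change declared.

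**Working it through.** No arithmetic applies. The check sets the definitions side by side and asks when they give the same count.

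**Inputs**

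| Item | Source | Refers to |
|---|---|---|
| Category to be summarized | SAP 16.1.2 title and first sentence | Study medication, permanently discontinued |
| Variable used to find it | SAP 16.1.2, AE-page question | Discontinuing from the study |
| Summary required | Protocol 9.4.7 | Study treatment |
| Item on drug action | Protocol 7.4.1.2.4, first bullet | Study medication: none, stopped, interrupted |
| Item on study exit | Protocol 7.4.1.2.4, second bullet | One level of other actions |

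**Cross-classification of one adverse event**

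| Medication stopped? | Left the study? | Belongs in a drug-stop category? | Counted under SAP 16.1.2? |
|---|---|---|---|
| Yes | Yes | Yes | Yes |
| Yes | No | Yes, subject to the meaning of permanent | No: missed |
| No | Yes | No | Yes: counted in error |
| No | No | No | No |

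The two definitions agree only if the middle rows are empty, that is, if every drug stop for an adverse event is also a study exit and every study exit for an adverse event is also a drug stop. Neither document states such a rule.

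**Can the middle rows occur?**

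- *Missed events.* Protocol 4.3.1 lists reasons for stopping treatment but does not say that the patient then leaves the study. Protocol 4.3.2 does not say so either. Staying on for assessments off treatment is neither described nor forbidden.
- *Events counted in error.* Periods are separated by 7 to 14 days without study medication. An adverse event in that gap that ends participation would be answered yes with no dose being taken. SAP 6.3 assigns such an event to the earlier period and the last treatment received, so it would appear as a drug stop on that treatment.

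**Do other outputs recover the information?** Partly.

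- SAP 13 takes the date of last study medication from the Disposition page's completion or discontinuation date, so exposure duration does not separate the two ideas.
- SAP 14 plans no compliance analysis.
- Vial accountability (SAP 13) is summarized by sequence and has no link to adverse events.
- SAP Appendix 1 says that CRF variables with data should be listed. A recorded drug stop should therefore remain visible in a listing, even if the summary omits it.

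**Is the better variable available?** Protocol 7.4.1.2 and 7.4.1.2.4 say that the item is assessed for each event, and protocol 8.3 says "Data for each patient will be recorded in an eCRF". That makes its presence on the AE page a reasonable inference, but the page itself is not among the documents.

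**The case against.** The strongest reply is that the SAP appears to treat stopping drug and leaving the study as the same event. SAP 13 dates the last dose from the Disposition page, and SAP 9 places discontinued or withdrawn patients in the last period attended. If the two always coincide, the table does not change. This stands as a possibility, but it is an unstated assumption and the protocol's separate items point the other way.

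Several stronger readings are tempting, and the documents do not support them:

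- *That patients who stop drug and return only for follow-up are lost.* Protocol 4.3.2 and 6.3.3.3 give early-terminated patients an end of study visit. Such a patient would be expected to be recorded as having left the study, and so would be counted.
- *That patients who stop in one period and are dosed in a later one are wrongly omitted.* SAP 16.1.2 speaks of permanent discontinuation. A patient dosed again has not permanently discontinued, so on the SAP's own wording the omission is consistent.
- *That both fields are certainly collected, so the change is only a swap of variable.* The SAP's yes/no question does not appear in that form in protocol 7.4.1.2.4, so the AE page is not a copy of that list. The SAP also cites protocol version 2.0, whereas the protocol supplied describes itself as the first version.
- *That drug stops will be under-reported to a known extent.* No rate is given, and the error can also inflate the count.

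Moving to the stopped level is not neutral either. That level carries no notion of permanence, so in a three-period crossover it could bring in stops confined to one period.

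**Conclusion.** The point holds as a mismatch between a safety category and the variable that defines it. SAP 16.1.2 does not, as written, deliver the summary that protocol 9.4.7 requires, and it can err in both directions. The size is unknown and may be nil. The effect is confined to this category, in its incidence table and the matching line of the overall AE summary. Listings should still show a recorded drug stop, and primary efficacy, power and the type I error rate are unaffected.

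The conclusion assumes that the AE items in protocol version 2.0 match those in the protocol supplied, and that no rule outside these documents makes every drug stop a study exit and the reverse. It does not rest on any claim that stops will in fact be missed.

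**What to change.** Before database lock:

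1. Confirm that action taken with study medication is an item on the AE page of the eCRF.
2. If it is, define the category in SAP 16.1.2 as TEAEs with that item at its stopped level.
3. Assign each such event to the treatment being taken when medication was stopped. This needs stating because SAP 16.1 allows one TEAE to be assigned to more than one treatment group.
4. State whether a stop confined to one crossover period counts, or only a stop with no later dosing in any period. If both are of interest, show both.
5. Keep the existing question and use it for a separate row of TEAEs leading to study discontinuation.
6. If the sponsor intends drug stop and study exit to coincide, say so in the SAP and reconcile the two fields before lock.

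The cost is a change of source variable, one sentence on permanence and one added row. No new data collection is needed if the item is on the AE page. If it is not, retitle the table as events leading to study discontinuation and record the departure from protocol 9.4.7 in SAP 3.3.

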16.1.3. SERIOUS ADVERSE EVENTS

Serious adverse events (SAEs) are those events recorded as "Serious" on the Adverse Events page of the eCRF. A summary of serious TEAEs by SOC and PT will be prepared.

16.1.4. ADVERSE EVENTS LEADING TO DEATH

TEAEs leading to Death are those events which are recorded as "Death" on the Adverse Events page of the eCRF. A summary of TEAEs leading to death by SOC and PT will be prepared.

16.2. LABORATORY EVALUATIONS

Results from the central laboratory will be included in the reporting of this study for hematology, blood chemistry and urinalysis. A list of laboratory assessments to be included in the outputs is included in the protocol, Sections 7.4.3.1, 7.4.3.2 and 7.4.3.3 for hematology, blood chemistry and urinalysis, respectively. Presentations will use SI Units.

Quantitative laboratory measurements reported as "< X", i.e. below the lower limit of quantification (BLQ), or "> X", i.e. above the upper limit of quantification (ULQ), will be converted to X for quantitative summaries, but will be presented as recorded, i.e. as "< X" or "> X" in the listings.

The following summaries will be provided for laboratory data:

- Actual and change from baseline (pre-dose at each treatment period) to each post-dose time point (for
 quantitative measurements), including overall (where overall is regardless of treatment period, day and
 timepoint to assess treatment group as a whole).
- Incidence of abnormal values according to normal range criteria
- Shift from baseline according to normal range criteria (for quantitative measurements and categorical

Document: Z:\RPL554\UYA25849\Biostatistics\Documentation\SAP\Verona RPL554-CO-204 SAP v1.0

Author: [name] Version Number: 1.0

Version Date: [18OCT2018]

Template No.: CS_TP_BS016 Revision 5 Reference: CS_WI_BS005

Effective Date: 01Apr2018

Page 38 of 50

measurements)

• Listing of abnormal values occurring after the first dose of study treatment.

16.2.1. LABORATORY REFERENCE RANGES AND MARKEDLY ABNORMAL CRITERIA

Quantitative laboratory measurements will be compared with the relevant laboratory reference ranges in SI units and categorized as:

- Low: Below the lower limit of the laboratory reference range.
- Normal: Within the laboratory reference range (upper and lower limit included).
- High: Above the upper limit of the laboratory reference range.

In addition to the high and low quantitative laboratory assignments (as identified by means of the laboratory reference ranges), markedly abnormal quantitative safety (and other) laboratory assessments will also be identified by the Investigator by manually annotating a print out of the results.

16.3. ECG EVALUATIONS

Overall results from the central ECG (Electrocardiogram) Reading Center will be included in the reporting of this study. The overall assessment of ECG parameters will be reported for this study:

- Normal
- Abnormal not Clinically Significant (ANCS)
- Abnormal Clinically Significant (ACS)

The following summaries will be provided for ECG data:

Actual assessments at baseline (pre-dose at each treatment period) and each post-dose time points, including
end of study visit and overall (where overall is regardless of treatment period, day and timepoint to assess
treatment group as a whole).

Document: Z:\RPL554\UYA25849\Biostatistics\Documentation\SAP\Verona RPL554-CO-204 SAP v1.0

Author: [name] Version Number: 1.0

Version Date: [18OCT2018]

Template No.: CS_TP_BS016 Revision 5 Reference: CS_WI_BS005

Effective Date: 01Apr2018

Page 39 of 50

- Shift of overall assessment baseline to post-dose time points according to markedly abnormal criteria
- Incidence of markedly abnormal criteria
- Listing of patients meeting markedly abnormal criteria

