9.3.2 Secondary Endpoints

- Change from baseline in trough FEV₁ on Day 4 (mean of -1 and 0 time prior to dosing)
- Determination of AUC_{0-4h} FEV₁ after morning dosing on Day 3
- Peak FEV₁ (measured in first 4 hours after dosing) and AUC_{0-12h} FEV₁. These will be measured after dosing on Day 1
- Change from baseline in AUC_{0-12h} FEV₁ measured on Day 3
- Change from pre-evening dose FEV₁ on Day 3 (peak over 4 hours)
- Determination of onset of action (>10% increase in FEV₁, from pre-first dose, censored at 120 minutes) on Day 1
- RV, FRC and sG_{aw} at 1.25 hours on Day 1 and 1.25, 8.25 and 12.25 hours after dosing on Day 3
- RPL554 steady state pharmacokinetics (AUC, C_{max} , time to maximum concentration [t_{max}])

Verona Pharma plc CONFIDENTIAL Page 49 of 66

- Safety and tolerability:
 - Continuous monitoring of adverse events
 - Laboratory safety tests [hematology, biochemistry and urinalysis]
 - 12-lead ECG (including QTcF and heart rate), supine vital signs [blood pressure and pulse rate]
 - Peak (measured in first 4 hours after dosing) and AUC_{0-4h} pulse rate for each treatment period.
 - Holter monitor results

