6.6. COMMON CALCULATIONS

For quantitative measurements, change from baseline will be calculated as:

• Test value at post-dose time point – pre-dose at each treatment period value.

Document: Z:\RPL554\UYA25849\Biostatistics\Documentation\SAP\Verona RPL554-CO-204 SAP v1.0

Author: [name] Version Number: 1.0

Version Date: [18OCT2018]

Template No.: CS_TP_BS016 Revision 5 Reference: CS_WI_BS005

Effective Date: 01Apr2018

Page 18 of 50

Peak effect will be calculated as:

Maximum value in the first 4 hours after dosing.

Average effect will be calculated as:

• FEV₁ AUC divided by the length of the time interval of interest.

Log-transformations will be performed on FEV₁ data:

- FEV₁ will be analyzed using multiplicative models, which means that data will be logged prior to analysis.
- The results will then be back-transformed to linear scale (treatment differences will thus be ratios of geometric means).
- Morning trough FEV₁ calculated as mean of the 11 and 12-hour FEV₁ measurements following the pre-evening dose.

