16.4. VITAL SIGNS

The following Vital Signs measurements will be reported for this study:

- Supine Systolic Blood Pressure (mmHg)
- Supine Diastolic Blood Pressure (mmHg)
- Supine Pulse Rate (bpm)

The following summaries will be provided for vital signs data:

 Actual assessments at screening, baseline (pre-dose at each treatment period) and each post-dose time points, including end of study visit and overall (where overall is regardless of treatment period, day and timepoint to assess treatment group as a whole).

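### Measured against the supplied protocol, SAP 16.3 and 16.4 list no output for QTcF, ECG heart rate, peak pulse rate or AUC0-4h pulse rate, and no change from baseline for vital signs

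*SAP*

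**What the plan says.** **Protocol.** Section 9.3.2 includes among its secondary safety endpoints "12-lead ECG (including QTcF and heart rate), supine vital signs [blood pressure and pulse rate" and, as a separate item, "Peak (measured in first 4 hours after dosing) and AUC_{0-4h} pulse rate for each treatment period". Section 9.4.7 covers laboratory tests, ECG and Holter parameters, vital signs and physical examination, and adds: "For continuous variables, the change from baseline (pre-dose at each treatment period) to each post-dose time point will also be calculated and summarized".

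**SAP, ECG.** Section 16.3 states: "The overall assessment of ECG parameters will be reported for this study". The levels are normal, abnormal but not clinically significant, and abnormal and clinically significant. The listed summaries are that category by time point, its shift from baseline, and the incidence and listing of *markedly abnormal* results. Neither QTcF nor heart rate appears anywhere in the SAP text.

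**SAP, vital signs.** Section 16.4 names supine systolic and diastolic pressure and pulse rate, with one summary item: "Actual assessments at screening, baseline (pre-dose at each treatment period) and each post-dose time points", plus the end-of-study and overall rows. For laboratory data, by contrast, SAP 16.2 asks for "Actual and change from baseline (pre-dose at each treatment period) to each post-dose time point".

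**SAP, changes.** Section 3.3 declares no change to the analysis from the protocol.

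**The concern.** The protocol promises quantitative cardiac endpoints, and the SAP sections that should deliver them list either a category or raw values. A three-level category cannot show how far QTcF moved. Two treatments could have the same count of clinically significant ECGs and quite different mean QTcF changes.

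Tolerability and safety of the combination is still a secondary objective in SAP 2.2, so the objective was kept while the named endpoints have no listed output. Protocol 1.2 notes a non-clinical potential for hypotension and tachycardia, and RPL554 is given here on top of a background product that contains a long-acting beta-agonist. An explicit, pre-specified summary of ECG intervals and rates is what a reader of the protocol would expect to find.

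**Working it through.** No power or effect-size calculation applies. The check sets each protocol quantity against the output lists in SAP 16.3 and 16.4, and then against any rule elsewhere in the SAP that could serve.

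| Protocol quantity | Output listed in SAP 16.3 or 16.4 | Rule elsewhere in the SAP |
|---|---|---|
| QTcF, value and change | none | change formula (6.6), period baseline (6.2) |
| ECG heart rate, value and change | none | same |
| Blood pressure | actual values; no change | same |
| Pulse rate | actual values; no change | same |
| Peak pulse rate, 0-4 h | none | generic peak rule (6.6) |
| AUC0-4h pulse rate | none | trapezoidal method (15.2.1.2), written for FEV1 |

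**Can the missing items be derived?** Mostly yes. SAP 6.2 sets the Day 1 pre-dose value of each period as baseline for post-dose safety endpoints. SAP 6.6 gives a change formula for quantitative measurements and a peak rule, "Maximum value in the first 4 hours after dosing", that is not tied to one variable. Its average rule is tied to FEV1: the words "AUC divided by the length of the time interval of interest" follow the name of that variable. SAP 15.2.1.2 sets out a trapezoidal formula with actual times, pre-dose taken as time 0, and a missing-data rule. Pulse rate could use it by reference, but no ECG or pulse-rate output calls any of these rules.

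**Does the day matter for the pulse-rate endpoints?** Protocol 9.3.2 names no day. Protocol 7.4.4 gives these post-dose readings up to 4 h:

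- Days 1 and 3: 0.5, 1, 2 and 4 h, which is 4 readings.
- Day 2: 0.5, 1, 2, 3 and 4 h, which is 5 readings.

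With pre-dose at time 0, the trapezoid intervals are 0.5 + 0.5 + 1 + 2 = 4 h on Days 1 and 3, and 0.5 + 0.5 + 1 + 1 + 1 = 4 h on Day 2. The 4 h reading then carries weight (2/2)/4 = 25% on Days 1 and 3, against (1/2)/4 = 12.5% on Day 2. The peak is likewise a maximum over 4 or 5 readings. The day therefore has to be stated for the endpoint to be fixed.

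**What still shows heart rate?** SAP 16.4 summarises supine pulse rate at period baseline and each post-dose time point. With complete data, mean change = mean at the time point minus mean at baseline, so a reader can recover the mean shift. The spread of the change cannot be recovered, because it depends on the within-patient correlation. SAP 16.6 summarises Holter results by treatment and time point. QTcF has no such substitute.

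**Is the one listed ECG output well defined?** Not fully. SAP 16.3 attributes the overall result to the central reading center. Protocol 7.4.6 has the investigator record that category in the eCRF and sends the recordings to a central vendor. The *markedly abnormal* criteria are explained in SAP 16.2.1 for laboratory values only.

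**The case against.** The strongest reply is that the comparison may use the wrong texts. SAP Section 1 says it is based on protocol version 2.0 of 10 July 2018, while the supplied protocol describes itself as the first version. SAP Section 8 leaves the format and content of tables to templates that were not supplied. Some wording has visibly moved: the SAP lists AUC0-8h FEV1 as a secondary variable, which protocol 9.3.2 does not. This stands as a limit. The declaration in SAP 3.3 cannot be tested against version 2.0, and the templates may already contain the outputs. It does not remove the gap, because the SAP is the document meant to say what is summarised, and nothing in it suggests that the safety endpoints were withdrawn.

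A second reply is that SAP 6.2, 6.6 and 15.2.1.2 already provide workable rules. That is largely right, and it makes the repair short. The outputs still have to be named, and the laboratory section shows that the SAP writes out change from baseline where it is wanted.

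A reader might infer that cardiac safety would go unreported. The documents do not support that: blood pressure and pulse rate by time point, Holter results, the ECG category and adverse events are all summarised. Nor do they show a heart-rate signal at the doses studied. Protocol 1.2 places the clinical increases at 12 to 24 mg, above the 1.5 and 6 mg used here, and reports no arrhythmogenic potential on Holter.

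A reader might also infer that the SAP omits required safety models, because the protocol synopsis mentions additive models for blood pressure, pulse rate and ECG heart rate. That is a mismatch within the protocol. Its Section 9.4.7 makes the safety analysis descriptive, and SAP Section 16 agrees by excluding treatment comparisons unless a section specifies one.

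**Conclusion.** The point holds as a gap in the SAP text relative to the supplied protocol. Four named secondary safety endpoints (QTcF, ECG heart rate, peak pulse rate and AUC0-4h pulse rate) have no listed output, and vital signs have no listed change from baseline, while SAP 3.3 declares no departure. If outputs follow the text, the main loss is the size of any QTcF shift. The loss for heart rate is partial, since pulse rate by time point and Holter results remain.

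This rests on two assumptions that the supplied documents cannot settle: that protocol version 2.0 keeps these endpoints, and that the templates do not already include the outputs. It would go too far to conclude that the sponsor dropped the endpoints or that SAP 3.3 is false. No loss of precision is claimed, because the documents give no variability for QTcF or pulse rate. The primary efficacy analysis is unaffected. The text should be corrected before unblinding; confidence is medium because of the two unseen documents.

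**What to change.** First check each item against protocol version 2.0 and the output templates. Then, before unblinding:

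1. **SAP 16.3.** Add actual values and change from period baseline for QTcF and ECG heart rate, by treatment and time point, from the central reading. State what defines *markedly abnormal* for ECGs, and whether the overall category is the investigator's or the reading center's.
2. **SAP 16.4.** Add change from period baseline for blood pressure and pulse rate. Derive and summarise peak pulse rate with the SAP 6.6 rule and AUC0-4h pulse rate by reference to the trapezoidal method in SAP 15.2.1.2. Name the day or days.
3. **SAP 3.3.** If any of these was deliberately dropped, record it with a reason. Note there too that the synopsis's additive models are not carried into the descriptive safety analysis. Safety models need not be added.

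The cost is SAP wording and a few extra descriptive tables. Protocol 8.3 has ECG data transferred electronically to the study database, and inclusion criterion 4 already needs numeric heart rate and QTcF. The documents do not say that numeric post-dose values are in the vendor transfer, so that must be confirmed.
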